14.1.3 Imaging logistics

- (*) Proportions of recruited participants not undergoing imaging with LDCT & CXR
- Time from CXR request to imaging & report, and reporting time by radiologist
- Incidences of unblinding (CXR)
- Total number of CT examinations (chest and other) undertaken per week
- Total number of CXR examinations (GP requested and total) undertaken per week
- Number of full-time equivalent radiographers and radiologists on rota per week.
- Proportion of CXR requests received that fulfil NG12 criteria on one day per week (week 1 = Monday, week 2 = Tuesday etc.)

14.1.4 Clinical outcomes

- (*) Prevalence of lung cancer among recruited patients
- Stage & histology of lung cancer at diagnosis
- Prevalence of indeterminate pulmonary nodules requiring CT surveillance
- Prevalence of incidental findings
- Subsequent investigations because of imaging (lung cancer and incidental findings)
- Eventual treatments for diagnoses resulting from imaging (lung cancer and incidental findings)
- Harms of investigation or treatment (including but not limited to invasive investigations or surgery for benign disease)

 Prospective validation (discrimination and calibration) of risk stratification to select patients for LDCT

14.2. WP2 Economic Outcomes

- Cost-effectiveness analysis of LDCT versus CXR, adapted from our model previously constructed on LDCT for asymptomatic patients by MEDLEY co-applicants and used in the recent UK NSC evaluation of lung cancer screening (35) evaluating strategies where all CXRs are replaced by LDCT, and also a targeted LDCT strategy (based on the 3% threshold).
- (*) Value of information assessment (including expected value of sample information) for a definitive trial considering total replacement of CXR with LDCT as well as targeted use of LDCT
- EQ-5D-5L at baseline and 4 months from all participants (including conversion to utility values with a suitable value set/tariff)
- Projected use (and cost) of subsequent investigations under counterfactual assumptions where only one imaging test (CXR or LDCT) is used

14.3. WP3 Qualitative outcomes

- Reasons for participating/not participating, barriers to participation and whether these contribute to disparities in recruitment
- Acceptability from patient perspective of:
 - Recruitment strategy
 - Trial design and imaging requirements
 - Proposed risk stratification of patients to receive LDCT instead of CXR
- Acceptability from GP perspectives including identifying site-level barriers and considering the impact of further investigations, treatments and additional diagnoses resulting from LDCT
- Perspectives and priorities of key stakeholders on post-trial implementation of instituting LDCT instead of CXR for lung cancer detection in routine primary care across the health system.

15 WP1 Statistical Considerations

15.1 Statistical Analysis Plan (SAP)

Statistical analysis is the responsibility of the CTRU Statisticians. A full statistical analysis plan (SAP) will be written according to published recommendations [37] before formal analyses are undertaken. The analysis plan will be written in accordance with current CTRU standard operating procedures and guidelines and will be finalised and agreed by the appropriate members of the research team and reviewed by the Study Oversight Committee (SOC). Any changes to the finalised analysis plan, together with reasons for changes will be fully documented. All analyses will be conducted using SAS version 9.4, unless stated otherwise.

Progression to the main study will be assessed after 5 months of recruitment, allowing for a 1-month decision period by the funder. Blinded interim reports will be presented to the SOC containing descriptive information. This will include data on recruitment, follow-up, safety and data quality.

A single final analysis will be conducted after the study is closed to recruitment and follow-up and when the full database has been cleaned and locked.

The main study population will include all participants registered to the study, regardless of postregistration activity.

A per protocol population, for pre-specified analyses, will consist of registered participants who complete both the LDCT and CXR tests within a maximum of 5 working days of each other (including MEDLEY PROTOCOL V2.0 04/12/2024

participants with indeterminate results) and have either a positive or negative cancer diagnosis at the end of the 12-month follow-up period.

15.1.1 Screening, flow of patients and baseline characteristics

The flow of participants and sites through the study will be presented in a modified Standards for Reporting of Diagnostic Accuracy Studies (STARD) diagram [38, 39], which will include numbers of potentially eligible patients, not eligible (with reasons), completing each of the index tests, positives/negatives on each test and reference standard results (with reasons where no reference standard is available).

Summary statistics will be presented for baseline participant characteristics by arm using means, standard deviations, medians, minimum, maximum, quartiles and range for continuous variables and counts and percentages for categorical variables.

In line with the STARD guidelines [39], the following items will also be reported:

- Distribution of lung cancer staging data
- Distribution of alternative diagnoses in participants without lung cancer
- Time interval and any clinical interventions between LDCT, CXR and the reference standard (cancer diagnosis within 12-months of clinical follow-up)

15.1.2 Analysis of outcomes

Continuous variables will be summarised using simple descriptive statistics, means, standard deviations, medians and ranges. Categorical variables will be summarised using counts and percentages, with proportions and confidence intervals reported as appropriate.

15.1.3 Feasibility outcomes

The monthly recruitment rate of participants to the study will be calculated by centre and overall. Point and precision estimates will be obtained for the recruitment rate using a log-linear Poisson regression model, with an offset term for total recruitment duration.

The number of participants who consent and who do not consent to participate in MEDLEY will each be divided by the number of patients screened who are eligible to take part in the study. A confidence interval for the proportion will be calculated using the exact method.

Centre performance will be summarised descriptively:

- Time from site approach (defined as date of issuing formal site selection email) to opening (defined as date of Sponsor Green Light to recruit email)
- Time from site opening to recruiting first participant
- Duration of site recruitment

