10.2. Eligibility Screening for WP1

Participating research sites will be required to complete a non-registration log of all patients who have been referred from general practice for CXR who fulfil the NG12 criteria and are considered potentially eligible for the study on the basis of their X-ray request but not recruited into the study. Documented reasons for ineligibility or declining participation will be collected and closely monitored by the CTRU as part of the regular review of recruitment progress. Non-registration logs should be returned to CTRU on a monthly basis. The following anonymised data will be collected on the non-registration log:

- Age
- Sex
- Index of multiple deprivation (according to participant's postcode)

- Ethnicity
- Date screened

Patients who are not registered either because they are ineligible or because they decline participation will also have the following recorded:

- Reason not eligible OR
- Reason declining participation
- Main language
- Whether or not the patient agrees to take part in WP3 including contact details and preferred method to receive further information

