10.3. WP1 Informed Consent and Eligibility

The Principal Investigator (PI) retains overall responsibility for the informed consent of participants at their site and must ensure that any person delegated responsibility to participate in the informed consent process is duly authorised, trained and competent to participate according to the ethically approved protocol, principles of Good Clinical Practice (GCP) and Declaration of Helsinki 1996. The assessment of eligibility will be confirmed and the informed consent process will be undertaken by the PI or registered healthcare professional who is approved by the PI as detailed on the Authorised Personnel Log.

Informed consent must be obtained prior to the participant undergoing procedures that are specifically for the purposes of the study and are out-with standard routine care at the participating site including the collection of identifiable participant data. Participants must remain free to withdraw at any time from all or some aspects of the study without having to give reasons and without prejudicing their further treatment. Participants must be provided with a contact point where they may obtain further information about the study.

Where a participant is required to re-consent or new information is required to be provided to a participant it is the responsibility of the PI to ensure this is done in a timely manner and according to any timelines requested by the CTRU.

Informed consent can be taken either (i) face-to-face on a paper form (written consent), (ii) as remote e-consent using REDCap, (iii) as remote verbal consent over the telephone. The mode of informed consent used will depend on the patient preference. Consent can be provided on the same day as NICE guidance stipulates imaging should be undertaken urgently (within 14 days) and as many centres now offer 'walk-in' appointments, patients typically proceed to have their CXR within a day or two of their consultation in primary care. There is minimal risk to the participant from the additional LDCT. The burden for participants is also minimal as there are no in person follow ups, imaging can be completed on the same day (or within 7 working days of each other), and each investigation is expected to take no more than 15 minutes.

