14.1.1 Outcomes relating to feasibility and deliverability of a definitive trial

- (*) Recruitment rate: number of participants recruited per centre-month
- (*) Proportions of eligible patients who consent/do not consent to participate, including assessment of non-participant characteristics associated with possible inequalities in participation
- (*) Time from site approach to opening, from opening to recruiting first participant, and duration of site recruitment

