15.2 Sample Size

Based on realistically recruiting 5 participants per site per week (i.e. 20 per site per month) and allowing staggered opening of sites, it is estimated that 900 participants can be recruited to MEDLEY within a 12-month recruitment timeframe. Recruiting a total of 900 patients will permit estimation of a per-centre-month recruitment rate for a full diagnostic accuracy trial and relevant trial sample size parameters with acceptable precision. For the recruitment rate, using generalised linear modelling theory, and working with the log-likelihood and Hessian for a one-parameter Poisson model, 900 participants gives a 2-sided 95% confidence interval for relative precision as (1/1.068 to 1.068) times the estimated rate. For example, with 20 participants per centre-month recruited, then a 95% confidence interval for the true recruitment rate would be (18.7 to 21.4) per centre-month. Based on 2021/22 -level data, between 250-579 CXRs per week per site are requested [25]. Our unpublished analysis indicates 31% of CXRs fulfil NG12 criteria, and experience with the Yorkshire Lung Screening Trial demonstrates 50% of eligible patients are recruited. Hence the average recruitment rate of five/week/centre is realistic.

Sensitivities of CXR and LDCT will be estimated. We anticipate that prevalence of lung cancer detected will be at least 1.7%. This is based on the proportion of those who were diagnosed with lung cancer within two years following investigation with CXR and with similar characteristics as participants who will be recruited to MEDLEY [40]. Although the follow up period for MEDLEY will be one year, rather than two years, the number of cancers detected will exceed that which would be identified on CXR alone and it is likely that a substantial proportion of cancers not detected on CXR would take longer than two years to be diagnosed [41].

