As a feasibility study, MEDLEY has not been designed for any pre-specified precision (which would be the design criteria for a definitive trial). With a prevalence estimated as 1.7%, an estimated sensitivity of 90% would have an 95% exact confidence interval covering values as low as 72% (estimated using the Clopper-Pearson exact method). Other metrics including specificity of CXR/LDCT, proportions of concordant/discordant imaging results, proportions completing imaging, and proportions completing questionnaires would all have 2-sided 95% confidence intervals +/- 3.3% (estimated using the normal approximation method) assuming that a minimum of 97% of participants are included in estimates of specificity, and assuming a worst-case estimate of 50% where estimated variance is maximised.

We have used simulation to predict how precisely we will estimate the proportion of CXR requests that fulfil NG12 criteria. Assuming that there will be at least 169 centre-weeks of recruitment and that for each of these, GP CXR requests will be assessed for NG12 and those eligible contacted until 5 potential recruits are identified, we expect to estimate the proportion of requests fulfilling NG12 with a 95% confidence interval width of 2.4%, with the interval width being below 3.0% with 90%

probability. The simulation incorporated uncertainty in the population proportion of CXR requests fulfilling NG12 criteria (Beta distribution with parameters 31 and 69) and the proportion of CXR requests which do fulfil NG12 criteria resulting in a potential recruit (Beta distribution with parameters 5 and 5).

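### The starred consent proportion can mix site reach with patients' willingness, because its denominator is screened eligible patients and the log has no category for those never asked

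*Protocol*

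**What the plan says.** Protocol section 14.1.1 lists "Proportions of eligible patients who consent/do not consent to participate" as a starred outcome and attaches to it an assessment of inequalities in participation. Section 14.0 explains that starred outcomes inform the decision to run a definitive trial, its design, or both.

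Section 15.1.3 fixes the calculation. The counts who consent and who do not "will each be divided by the number of patients screened who are eligible to take part in the study". The protocol does not define screened.

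Section 10.2 sets the data collection. Sites must "complete a non-registration log of all patients who have been referred from general practice for CXR who fulfil the NG12 criteria" and who look potentially eligible from the request but are not recruited. Age, sex, deprivation, ethnicity and screening date are recorded for everyone on the log. The section then adds: "Patients who are not registered either because they are ineligible or because they decline participation will also have the following recorded". The items that follow are a reason for ineligibility or for declining, main language, and willingness to join WP3.

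Section 15.2, describing a simulation, assumes requests are assessed and "those eligible contacted until 5 potential recruits are identified" in each centre-week.

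**The concern.** A logged patient may be neither ineligible nor a decliner. The wording of section 10.2 allows for this but gives such a patient no reason field and no main-language entry.

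The protocol also shows how the group arises. Section 10.3 notes that many centres offer walk-in appointments and that "patients typically proceed to have their CXR within a day or two of their consultation in primary care". Sections 12.2 and 12.4 require the LDCT before the CXR, so a patient already X-rayed cannot follow the schedule, yet no criterion in 9.1 or 9.2 makes that patient ineligible. Others cannot be reached, or are not called because enough recruits have been found. The flow diagram items in section 15.1.1 include no count of patients approached.

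If these patients are in the denominator, a low consent proportion could mean that people refuse or that sites did not ask. These call for different remedies in a definitive trial, overall and within deprivation or ethnic groups. If the reason for not asking is not collected, no later analysis plan can recover it.

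**Working it through.** **The plan's own figures.** The protocol gives no expected consent proportion. Its neighbouring figures in section 15.2 reproduce:

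- Recruitment-rate precision: exp(1.96/√900) = 1.068, and 20/1.068 to 20 × 1.068 gives 18.7 to 21.4 per centre-month, as stated.
- NG12 simulation (169 centre-weeks, stop at five potential recruits, Beta(31,69) and Beta(5,5)), rerun 40,000 times: mean interval width 2.41% against the stated 2.4%; probability of a width below 3.0% is 0.885 against the stated 90%. Median eligible patients contacted is 10.0 per centre-week.

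**Inputs, all from section 15.2.** "between 250-579 CXRs per week per site are requested"; "31% of CXRs fulfil NG12 criteria"; uptake of 50% among eligible patients, taken from a lung screening trial; five recruits per centre per week.

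**Reading A: only patients worked through under the stopping rule are screened.**

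- Approached per centre-week: 5/0.50 = 10.
- Proportion: 5/10 = 50%. For 900 of 1,800, the exact 95% interval is 47.7% to 52.3%.

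**Reading B: the whole NG12 pool (log plus recruits) is screened, and all are treated as eligible.**

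- Pool per centre-week: 250 × 0.31 = 77.5; 579 × 0.31 = 179.5.
- Proportion: 5/77.5 = 6.5%; 5/179.5 = 2.8%.
- Relative to 50%: 7.8 to 17.9 times lower.

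**Reading B with some patients failing the other criteria (the shares are assumptions).**

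| Share of NG12 patients eligible | Pool per centre-week | Consent proportion | Times below 50% |
|---|---|---|---|
| 100% | 77.5 to 179.5 | 6.5% to 2.8% | 7.8 to 17.9 |
| 50% | 38.8 to 89.7 | 12.9% to 5.6% | 3.9 to 9.0 |
| 25% | 19.4 to 44.9 | 25.8% to 11.1% | 1.9 to 4.5 |

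**In general.** If a share u of the denominator was never offered the study, the observed proportion is 0.50 × (1 − u). A three-fold understatement needs u of about two thirds.

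**Residual dilution under Reading A.** Unreachable or already-imaged patients can remain even with the stopping rule. If there were 5 to 10 of them per centre-week (an assumption), the proportion would be 5/15 = 33% to 5/20 = 25%.

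**The case against.** A reader might infer that patients never asked are counted as non-consenters. The protocol does not say so. Section 15.1.3 gives those who do not consent their own numerator, so unapproached patients could be in the denominator only, and the two proportions would then not sum to 100%. The consent proportion is diluted either way.

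A reader might also take 3% to 6% as the expected result. Three points count against that, and all stand:

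- The log holds patients who look potentially eligible from a request, whereas the denominator is eligible patients. Section 10.3 has eligibility confirmed by the PI or an approved professional, and several exclusions in 9.2 need not show on a CXR request.
- Under the stopping rule in 15.2, requests after the fifth potential recruit would not be screened, and most of the dilution goes.
- Sections 12.10 and 14.1.3 sample the NG12 share on one day a week at selected sites, which suggests that sites are not expected to assess every request.

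Nor does the log hide refusals. Decliners are identifiable by their recorded reason, and a logged patient with neither reason is a distinguishable remainder. What is lost is why that remainder was not asked.

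Finally, code lists and working definitions are often left to the analysis plan or the case report form, and uptake among screened eligible patients is a legitimate feasibility measure. That is fair, but the denominator and the log's reason fields are stated here rather than deferred. The stopping rule is a simulation assumption, whereas section 10.2 is the instruction to sites and says all patients. Nothing reconciles the two.

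**Conclusion.** The point holds as a problem of definition and data collection in a starred outcome. As written, the consent proportion can combine how many patients a site reaches with how many agree, and the log does not record why a potentially eligible patient was not asked.

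The size is undetermined. It is about 50% under the stopping rule, 2.8% to 6.5% in the extreme case, and in between on intermediate assumptions. Sites that read the log instruction differently would also not be comparable.

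These figures assume that the 250 to 579 requests are GP requests, that the borrowed 50% uptake applies to patients approached, and that each potential recruit consents. The documents do not support the stronger claims that unapproached patients are classed as refusals or that a figure of a few per cent is to be expected. This is a cheap improvement.

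**What to change.** 1. State in sections 10.2 and 15.1.3 which patients count as screened, and reconcile the instruction to log all patients with the stop at five potential recruits in 15.2.
2. Add a log category for potentially eligible but not approached, with a coded reason: quota reached, not contactable, CXR already done, or no staff or scanner slot.
3. Beside the existing proportion, report approached/potentially eligible (reach) and consented/approached (willingness). Use the latter as the measure of willingness when deciding on a definitive trial.
4. Run the inequality comparison separately for patients not approached and for those approached who declined.

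The cost is one coded field, a reworded denominator and slightly more logging at sites.

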9.1. Inclusion Criteria for WP1

Patients meeting ALL the following criteria will be considered for enrolment into the study.

- 1. Age 40 years or more at the time the consent form is signed.
- 2. Have had a CXR requested in general practice which fulfils NICE NG12 criteria [6]
- 3. Consent to participate in WP1 (written/verbal/eConsent).

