9.2. Exclusion Criteria for WP1

Patients will be excluded from this study for ANY of the following reasons:

- 1. Present with haemoptysis and/or have a pending urgent suspected cancer referral.
- 2. Have had thoracic CT or LDCT within the last year
- 3. Unable to, or chooses not to, receive a LDCT
- 4. Currently undergoing anti-cancer treatment.
- 5. Is pregnant* or currently breastfeeding.
- 6. Previously registered in the MEDLEY study

*Assessment of pregnancy potential (or exemption) completed as per national guidelines and/or local Trust policy.

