9.3. Patient, GP, and Stakeholder Eligibility for WP3

For patients:

- 1. Met the first two inclusion criteria listed in Section 9.1.
- 2. Consent to participate in WP3 (written/verbal/e-consent informed consent) Note: patients who decline to participate in WP1 will still be given the opportunity to take part in WP3 (see section 10.4)
- 3. Do not meet exclusion criteria 1, 2, 4, or 5 in Section 9.2

For GPs:

1. Consent to participate in WP3 (written/verbal/e-consent informed consent). MEDLEY PROTOCOL V2.0 04/12/2024

- 2. Current practicing General Practitioner.
- 3. Either
 - a) Has referred a patient for a chest X-ray who was subsequently consented to WP1 OR
 - b) Has referred a patient meeting NG12 criteria for CXR

For stakeholders:

- 1. Consent to participate in WP3 (written/verbal/e-consent informed consent).
- 2. Relevant professional background, including:
 - Clinician in respiratory medicine, radiology, and radiography
 - senior leaders invited from professional organisations (e.g. Royal College of Radiologists, UK Lung Cancer Coalition)
 - commissioners (e.g. Integrated Care Boards)
 - policy makers (e.g. NHS England)
 - patient advocacy groups.

10.0 Recruitment

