14.0 Outcome Measures

Outcomes are grouped according to type and those marked with an asterisk (*) will inform the decision to proceed to, and/ or inform the design of a definitive trial.

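### The consent proportion is taken among eligible patients, but exclusion 3 makes a patient who does not want the LDCT ineligible, so applied as written LDCT refusals leave the denominator and uptake is overstated

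*Protocol*

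**What the plan says.** - **Outcome.** Section 14.1.1 lists, with an asterisk, "Proportions of eligible patients who consent/do not consent to participate, including assessment of non-participant characteristics associated with possible inequalities in participation". Section 14.0 explains that asterisked outcomes "will inform the decision to proceed to, and/ or inform the design of a definitive trial".
- **Analysis.** Section 15.1.3 counts consenters and non-consenters, each "divided by the number of patients screened who are eligible to take part in the study", with an exact confidence interval.
- **Eligibility.** Exclusion 3 in Section 9.2, repeated in the Section 4.0 summary, reads "Unable to, or chooses not to, receive a LDCT". It joins an inability and a choice in one criterion. The exclusion list in the Section 5.0 flow diagram omits it.
- **Log.** Section 10.2 says: "Patients who are not registered either because they are ineligible or because they decline participation will also have the following recorded". A reason for ineligibility or a reason for declining is then entered. No rule says which applies to someone who does not want the LDCT.
- **Planning value.** Section 15.2 expects 50% of eligible patients to be recruited, citing experience from a lung screening trial, and plans 900 participants.

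**The concern.** Section 10.1.1 says the study pathway departs from standard care only in consent, data collection and the LDCT. Not wanting the LDCT is therefore one of the most direct reasons a patient can have for declining. Inability to have the scan is a genuine eligibility matter; unwillingness is a consent decision. Exclusion 3 treats both as ineligibility, and the analysis then restricts itself to eligible patients, so the refusals most specific to this study can disappear from its measure of uptake.

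The definitive trial would ask patients to accept the same scan. An uptake figure that leaves out those who refuse it would make the number to be screened per recruit look smaller than it is. If some centres log these patients as ineligible and others as declining, between-centre differences in consent would partly reflect coding.

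**Working it through.** **Nearest stated figure.** The protocol gives no precision for the consent proportion. Its nearest feasibility figure is the recruitment-rate interval in Section 15.2: exp(1.96/√900) = exp(0.0653) = 1.0675, so 20/1.0675 = 18.7 and 20 × 1.0675 = 21.4 per centre-month. This reproduces the stated factor of 1.068 and the interval 18.7 to 21.4. The present issue does not affect it.

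**Direction.** Let C be consenters, D patients who decline for other reasons, and R patients who meet every other criterion but do not want the LDCT.

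- Rule as written: C/(C + D)
- LDCT refusals kept in: C/(C + D + R)

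For any R > 0 the first exceeds the second, so the rule as written can only raise the proportion.

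**Size, as illustration.** Inputs from the protocol: 900 recruits and 50% uptake, hence 900 consenters and 900 non-consenters. Assumed, because the protocol gives no figure: the share f of the 900 non-consenters who refuse because of the LDCT. The rule as written gives 900/(1800 − 900f). Intervals are exact (Clopper-Pearson) 95%.

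| f (assumed) | LDCT refusals | Denominator as written | Reported consent | 95% CI |
|---|---|---|---|---|
| 0% | 0 | 1800 | 50.0% | 47.7 to 52.3 |
| 10% | 90 | 1710 | 52.6% | 50.2 to 55.0 |
| 20% | 180 | 1620 | 55.6% | 53.1 to 58.0 |
| 30% | 270 | 1530 | 58.8% | 56.3 to 61.3 |
| 50% | 450 | 1350 | 66.7% | 64.1 to 69.2 |

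With the refusals kept in, every row would read 900/1800 = 50.0% (47.7 to 52.3). From the 20% row upwards the two intervals no longer overlap. The reported non-consent proportion falls correspondingly, from 50.0% to 47.4% at f = 10% and 33.3% at f = 50%.

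**The other base.** If 50% is instead taken as the result under the written rule, adding back 90, 180 or 450 refusals gives 900/1890 = 47.6%, 900/1980 = 45.5% or 900/2250 = 40.0%. The direction is the same.

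**Between centres.** Take two centres whose patients behave identically, with f = 20%. The one that logs LDCT refusals as ineligible reports 55.6%; the one that logs them as declining reports 50.0%.

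**The case against.** The strongest reply is that Section 10.2 never assigns an LDCT refusal to the ineligible category. A site may naturally log it as declining, and then nothing is lost. That is correct as to what the log says, and the bias is not certain to occur in practice. But it depends on sites departing from exclusion 3, and no section tells them to or returns these patients to the denominator.

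Much of the information also survives. Age, sex, deprivation and ethnicity are logged for non-registered patients whether ineligible or declining, and ineligibility reasons appear in the STARD diagram (15.1.1). LDCT opt-outs after registration are counted under imaging logistics. This lessens the harm but does not correct the estimate in 15.1.3, and the split can be recovered later only if the recorded reason separates inability from unwillingness.

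A reader might infer more than the protocol supports:

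- **That the proportion must be 100%, because consent is itself inclusion criterion 3.** Sections 14.1.1 and 15.1.3 expressly count eligible patients who do not consent, so their use of eligible cannot include that criterion.
- **That acceptability is overstated.** Acceptability and reasons for not participating are WP3 outcomes (14.3), and WP3 can interview LDCT refusers. The affected quantity is uptake.
- **That WP3 shows the team regards LDCT refusers as decliners.** WP3 patients must satisfy "Do not meet exclusion criteria 1, 2, 4, or 5 in Section 9.2", which omits criterion 6 as well as 3, so it says little about how refusers are classed in WP1.
- **That the inequality assessment is distorted.** It is worded around non-participants, whose characteristics are logged either way; distortion is not shown.
- **That this proportion decides progression.** It informs the decision or the design. No threshold attaches to it, and the pilot criteria in Section 8.4 use recruitment numbers, rate and open centres.

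**Conclusion.** The point holds for the consent proportion. Sections 9.2 and 15.1.3, followed as written, remove LDCT refusals from the denominator of an asterisked outcome and bias uptake upward. Because the log does not settle the coding, the proportion may also not be comparable across centres. The direction follows from the definitions; the size does not. The range of 52.6% to 66.7% against 50% rests on assumed refusal shares of 10% to 50% and on an uptake figure borrowed from a screening trial, so it is not a forecast for this study. The recruitment rate, the pilot criteria and the WP3 acceptability findings are unaffected. This should be corrected, ideally before many log entries accumulate, but it does not threaten the study as a whole.

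**What to change.** 1. On the non-registration log (10.2), give two separate codes: unable to have the LDCT, classed as ineligible; and does not want the LDCT, classed as declined.
2. In 15.1.3, define the denominator as screened patients who meet inclusion criteria 1 and 2 and have no exclusion other than choosing against the LDCT. Count those who choose against it as non-consenters, and state that inclusion 3 (consent) is not required for the denominator.
3. Make 14.1.1 refer to the same definition.

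Under this definition the result no longer depends on whether a site records the LDCT or some other reason for declining, since both count as non-consent. The eligibility criteria need not be rewritten and no patient is managed differently. The cost is a log code, a short definition, a coding instruction to centres and, if logs have already been returned, a check of earlier entries. The reported consent proportion will be lower than under the present wording if any patient refuses because of the LDCT.
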